8.3 ADVERSE EVENTS AND SERIOUS ADVERSE EVENTS

8.3.1 DEFINITION OF ADVERSE EVENTS (AE)

Adverse event means any untoward medical occurrence associated with the use of an intervention in humans, whether or not considered intervention-related (21 CFR 312.32 (a)).

In this study, there are predefined "common expected post-treatment effects" that should be transient (i.e., lasts less than 24 hours): erythema, warmth, and edema at the treated sites. These effects will be recorded on CRFs on safety monitoring, but will not be considered AEs unless the effect

persists longer than expected (i.e., does not resolve within 24 hours of treatment administration) or meets the definition of a serious AE.

Close attention will be paid to any incidences of cutaneous blistering at the treated sites, either within the incision sites or on the peri-incisional skin.

8.3.2 DEFINITION OF SERIOUS ADVERSE EVENTS (SAE)

An adverse event (AE) or suspected adverse reaction is considered "serious" if, in the view of either the investigator or sponsor, it results in any of the following outcomes: death, a life-threatening adverse event, inpatient hospitalization or prolongation of existing hospitalization, or a persistent or significant incapacity or substantial disruption of the ability to conduct normal life functions. Important medical events that may not result in death, be life-threatening, or require hospitalization may be considered serious when, based upon appropriate medical judgment, they may jeopardize the participant and may require medical or surgical intervention to prevent one of the outcomes listed in this definition.

8.3.3 CLASSIFICATION OF AN ADVERSE EVENT

8.3.3.1 SEVERITY OF EVENT

For AEs not included in the protocol defined grading system, the following guidelines will be used to describe severity.

- **Mild** Events require minimal or no treatment and do not interfere with the participant's daily activities.
- **Moderate** Events result in a low level of inconvenience or concern with the therapeutic measures. Moderate events may cause some interference with functioning.
- Severe Events interrupt a participant's usual daily activity and may require systemic drug therapy or other treatment. Severe events are usually potentially life-threatening or incapacitating. Of note, the term "severe" does not necessarily equate to "serious".

8.3.3.2 RELATIONSHIP TO STUDY INTERVENTION

All AEs must have their relationship to study intervention assessed by the clinician who examines and evaluates the participant based on temporal relationship and his/her clinical judgment. The degree of certainty about causality will be graded using the categories below. In a clinical trial, the study product must always be suspect.

- **Definitely Related** There is clear evidence to suggest a causal relationship, and other possible contributing factors can be ruled out. The clinical event occurs in a plausible time relationship to study intervention administration and cannot be explained by concurrent disease or other drugs or chemicals. The response to withdrawal of the study intervention (dechallenge) should be clinically plausible. The event must be pharmacologically or phenomenologically definitive, with use of a satisfactory rechallenge procedure if necessary.
- Probably Related There is evidence to suggest a causal relationship, and the influence of other factors is unlikely. The clinical event occurs within a reasonable time after administration of the study intervention, is unlikely to be attributed to concurrent disease or

other drugs or chemicals, and follows a clinically reasonable response on withdrawal (dechallenge). Rechallenge information is not required to fulfill this definition.

- **Potentially Related** There is some evidence to suggest a causal relationship (e.g., the event occurred within a reasonable time after administration of the trial medication). However, other factors may have contributed to the event (e.g., the subject's clinical condition, other concomitant events). Although an AE may rate only as "possibly related" soon after discovery, it can be flagged as requiring more information and later be upgraded to "probably related" or "definitely related", as appropriate.
- Unlikely to be related A clinical event whose temporal relationship to study intervention administration makes a causal relationship improbable (e.g., the event did not occur within a reasonable time after administration of the study intervention) and in which other drugs or chemicals or underlying disease provides plausible explanations (e.g., the subject's clinical condition, other concomitant treatments).
- Not Related The AE is completely independent of study intervention administration, and/or evidence exists that the event is definitely related to another etiology. There must be an alternative, definitive etiology documented by the clinician.

If there is any doubt as to whether a clinical observation is an AE, the event will be reported. Evaluation of relatedness will consider etiologies such as natural history of the underlying disease, concurrent illness, concomitant therapy, study-related procedures, accidents, and other external factors.

8.3.3.3 EXPECTEDNESS

The PI will be responsible for determining whether an AE is expected or unexpected. An AE will be considered unexpected if the nature, severity, or frequency of the event is not consistent with the risk information previously described for the study intervention.

8.3.4 TIME PERIOD AND FREQUENCY FOR EVENT ASSESSMENT AND FOLLOW-UP

The occurrence of an AE or SAE may come to the attention of study personnel during study visits and interviews of a study participant presenting for medical care, or upon review by a study monitor.

All AEs including local and systemic reactions not meeting the criteria for SAEs will be captured on the appropriate CRF. Information to be collected includes event description, time of onset, clinician's assessment of severity, relationship to the study intervention (assessed only by those with the training and authority to make a diagnosis), and time of resolution/stabilization of the event. All AEs occurring while on study must be documented appropriately regardless of relationship. All AEs will be followed to adequate resolution.

Any medical condition that is present at the time that the participant is screened will be considered as baseline and not reported as an AE. However, if the study participant's condition deteriorates at any time during the study, it will be recorded as an AE.

Changes in the severity of an AE will be documented to allow an assessment of the duration of the event at each level of severity to be performed. AEs characterized as intermittent require documentation of onset and duration of each episode.

The investigators will record all reportable events with start dates occurring any time after informed consent is obtained until 7 (for non-serious AEs) or 30 days (for SAEs) after the last day of study participation. At each study visit, the investigator will inquire about the occurrence of AE/SAEs since the last visit. Events will be followed for outcome information until resolution or stabilization.

[figure not shown]
8.3.5 ADVERSE EVENT REPORTING

All required reportable events must be reported to the IRB within the deadlines specified in the SUNY Downstate Medical Center Policy IRB-01: Human Research Protections Program. Unanticipated adverse device effects (UADEs) will be reported as soon as possible, but no later than 10 days.

Any AEs that occur in-office during or immediately after treatment sessions, or reported by the subject in the AE diary or in weekly phone calls, will be captured on the appropriate CRF. Information to be collected includes a description of the AE, time of onset, severity, relationship to the study intervention, and time of resolution/stabilization.

Subjects will be counseled regarding the expected outcome of skin erythema and warmth, found to resolve within 24 hours in other clinical studies and occurs in 10% of participants.^{70,71} For this study, the common expected post-treatment side effects of transient erythema, warmth, and swelling at the treated sites will be recorded, but will not be considered an AE for the purposes of safety reports.

All AEs will be reported to the designated medical monitor ([name]), independent safety monitor ([name]), and internal faculty committee at monthly meetings. Please refer to *Section 10.1.6: Safety Oversight* for the composition of the internal committee. [name] is the Director of Clinical Trials & Research in the Department of Dermatology at SUNY Downstate whose responsibilities include: managing and ensuring research compliance; monitoring all departmental clinical trials for AEs; and overseeing appropriate reporting of AEs to the IRB. AEs will be reported to the IRB, NIH, and FDA on a quarterly basis. The PI is responsible for completing and signing off on the AE reports.

[figure not shown]
8.3.6 SERIOUS ADVERSE EVENT REPORTING

The study clinician will immediately report to the sponsor any SAE, whether or not considered study intervention related, including those listed in the protocol and must include an assessment of whether there is a reasonable possibility that the study intervention caused the event. Study endpoints that are SAEs must be reported in accordance with the protocol unless there is evidence suggesting a causal relationship between the study intervention and the event. In that case, the investigator must immediately report the event to the sponsor.

All SAEs will be followed until satisfactory resolution or until the site investigator deems the event to be chronic or the participant is stable. Other supporting documentation of the event may be requested by the study sponsor and should be provided as soon as possible.

If applicable, the study investigator shall complete an Unanticipated Adverse Device Effect Form and submit to the study sponsor and to the reviewing IRB as soon as possible, but in no event later than 10 working days after the investigator first learns of the effect. The study sponsor is responsible for conducting an evaluation of an unanticipated adverse device effect and shall report the results of such evaluation to the FDA and to all reviewing IRBs and participating investigators within 10 working days after the sponsor first receives notice of the effect. Thereafter, the sponsor shall submit such additional reports concerning the effect as FDA requests.

Per SUNY Downstate policy for clinical trials, SAEs must be reported within 24 hours if an internal AE is serious, unanticipated, and would have implications for the conduct of the study. For this study, SAEs will be reported to the designated medical monitor ([name]), safety officer ([name]) and the reviewing IRB on the same day of learning of the event. SAEs will be reported to the FDA and the NIH within 48 hours by express mail. The PI is responsible for completing and signing off on the SAE reports.

8.3.7 REPORTING EVENTS TO PARTICIPANTS

N/A

8.3.8 EVENTS OF SPECIAL INTEREST

N/A

8.3.9 REPORTING OF PREGNANCY

N/A

8.4 UNANTICIPATED PROBLEMS

8.4.1 DEFINITION OF UNANTICIPATED PROBLEMS (UP)

The Office for Human Research Protections (OHRP) considers unanticipated problems (UPs) involving risks to participants or others to include, in general, any incident, experience, or outcome that meets all of the following criteria:

LED-Red Light Phototherapy for Skin Scarring Prevention IRB# 1304108

- Unexpected in terms of nature, severity, or frequency given (a) the research procedures that are described in the protocol-related documents, such as IRB-approved research protocol and informed consent document; and (b) the characteristics of the participant population being studied;
- Related or possibly related to participation in the research ("possibly related" means there is a reasonable possibility that the incident, experience, or outcome may have been caused by the procedures involved in the research); and
- Suggests that the research places participants or others at a greater risk of harm (including physical, psychological, economic, or social harm) than was previously known or recognized.

This definition could include an unanticipated adverse device effect, any SAE on health or safety or any life-threatening problem or death caused by, or associated with, a device, if that effect, problem, or death was not previously identified in nature, severity, or degree of incidence in the investigational plan or application (including a supplementary plan or application), or any other unanticipated serious problem associated with a device that relates to the rights, safety, or welfare of subjects (21 CFR 812.3(s)).

8.4.2 UNANTICIPATED PROBLEM REPORTING

The investigator will report UPs to the reviewing IRB and to the PI. The UP report will include the following information:

- Protocol identifying information: protocol title and number, PI's name, and the IRB project number;
- A detailed description of the event, incident, experience, or outcome;
- An explanation of the basis for determining that the event, incident, experience, or outcome represents an UP;
- A description of any changes to the protocol or other corrective actions that have been taken or are proposed in response to the UP.

To satisfy the requirement for prompt reporting, UPs will be reported using the following timeline:

- UPs that are SAEs will be reported to the IRB on the same day of the investigator becoming aware of the event and to the study sponsor within 48 hours.
- Any other UP will be reported to the IRB and to the study sponsor within 10 working days of the investigator becoming aware of the problem.
- All UPs should be reported to appropriate institutional officials (as required by an institution's written reporting procedures), the supporting agency head (or designee), and the OHRP within 10 working days of the IRB's receipt of the report of the problem from the investigator.

An investigator shall submit to the sponsor and to the reviewing IRB a report of any unanticipated adverse device effect occurring during an investigation as soon as possible, but in no event later than 10 working days after the investigator first learns of the effect (21 CFR 812.150(a)(1)). A sponsor who conducts an evaluation of an unanticipated adverse device effect under 812.46(b) shall report the results of such evaluation to the FDA and to all reviewing IRB's and participating investigators within 10 working days after the sponsor first receives notice of the effect. Thereafter the sponsor shall submit such additional reports concerning the effect as FDA requests (21 CFR 812.150(b)(1)).

8.4.3 REPORTING UNANTICIPATED PROBLEMS TO PARTICIPANTS

N/A

9 STATISTICAL CONSIDERATIONS

9.1 STATISTICAL HYPOTHESES

- Hypothesis for Primary Efficacy Endpoint: There is a statistically significant difference in scar pliability between a LED-RL-treated incision and a mock-treated incision.
 - Skin elasticity and induration (an index of scar pliability) are measured pre-treatment at the first treatment session and post-treatment on follow-up visits at POD 30, 90, and 180.
- Hypothesis for Secondary Efficacy Endpoint(s): LED-RL phototherapy treatment results in a statistically significant improvement in POSAS score and VAS score compared to mock treatment.

9.2 SAMPLE SIZE DETERMINATION

The study will have three treatment arms (LED-RL 160 J/cm², LED-RL 320 J/cm², and LED-RL 480 J/cm²) with 10 subjects each. The primary outcome measure is the difference in pliability between a treated incision site and the contralateral mock-treated incision site.

To calculate the sample size for this study, we anticipate that the minimal clinically important difference in scar pliability is 15%, based on minimum decrease in fibroblast cell number after LED-RL treatment from our *in vitro* data. A power analysis plan predicted that with 9 subjects, the study would have greater than 80% power to detect a 15% difference in pliability by using a two-sided paired *t*-test. To take into account a dropout rate of 10%, 10 subjects will be enrolled in each treatment arm. Up to 150 potential participants will be screened and a total of 30 subjects will be enrolled in the study.

9.3 POPULATIONS FOR ANALYSES

- Intention-to-treat (ITT) analysis dataset: all participants who are enrolled and randomly allocated to treatment, regardless of treatment actually receive
- Per-protocol analysis dataset: participants who adhered to the protocol and completed the treatment originally allocated (i.e., attended all treatment sessions)
- Safety analysis dataset: participants who received at least one dose of the study intervention

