1.2 SCHEMA

1.3 SCHEDULE OF ACTIVITIES (SOA)

Procedures	Screening within 6 weeks	prior to surgery	Enrollment at 24 hours after screening	Baseline/day of surgery (Visit 1)	Treatment #1 (Visit 2)	Treatment #2 (Visit 3)	Treatment #3 (Visit 4)	Treatment #4 (Visit 5)	Treatment #5 (Visit 6)	Treatment #6 (Visit 7)	Treatment #7 (Visit 8)	Treatment #8 (Visit 9)	Treatment #9 (Visit 10)	Follow-up at POD 30 + 1 week (Visit 11)	Follow-up at POD 90 + 1 week (Visit 12)	Final study visit at POD 180 + 1 week (Visit 13)
Informed consent	Х															
Demographics	Х															
Medical history	Х			Х												
Concomitant medication review	Х			х	х	х	х	х	х	х	х	х	х			
Targeted physical exam of skin	х		х	х	х	х	х	х	х	х	х	х	х	х	х	х
Conduct screening photosensitivity test	х															
Evaluate for photosensitivity			х													
Adverse event review and evaluation			х		х	х	х	х	х	х	х	х	х	х	х	х
Randomization			Х													
Mini-facelift surgery				Х												
Administer study intervention (LED-RL and mock therapy)					х	х	x	х	х	х	х	х	x			
Digital photography				Х	Х	Х	Х	Х	Х	Х	Х	Х	Х	Х	Х	Х
Skin biopsy (optional)				Х										Х		
ОСТ					Х									Х	Х	Х
Skin elasticity and induration measurements					х									х	х	х
Collagen and water concentration measurements					x									х	х	х
Skin imaging analysis		+			Х									Х	х	х
POSAS		+			X									X	X	X
Complete case report forms	х		х	х	x	х	х	х	х	х	х	х	х	x	x	x
Exit questionnaire																Х

Screening Visit (within 6 weeks prior to surgery)

- Obtain written informed consent.
- Verify that the potential subject has opted to undergo elective mini-facelift surgery.
- Review medical history by interview to determine eligibility based on inclusion/exclusion criteria.
- Review list of current medications to determine eligibility based on inclusion/exclusion criteria.

- Perform targeted physical examination of skin. For this study, potential subjects must have excess lax facial skin that is suitable for mini-facelift surgery, as determined by the surgeon's clinical assessment. Potential subjects also cannot have any open wounds, pre-existing scars, fibrotic skin disease, or other medical conditions affecting the periauricular skin (i.e., the site of the surgical incisions and of the proposed LED-RL treatment).

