5.5 STRATEGIES FOR RECRUITMENT AND RETENTION

Potential subjects who are interested in elective mini-facelift surgery will be recruited through IRBapproved flyers on bulletin boards, physician referrals, websites (SUNY Downstate Department of Dermatology webpage, SUNY Downstate Clinical and Translational Science Center "Clinical Trials List", StudyPages.com, and ClinicalTrials.gov), social media, website ads, radio ads, and/or newspaper ads. Potential participants will be identified by their expressed interest in a mini-facelift or perceived suitability for the surgery (i.e., they have excess lax facial skin and desire a mini-facelift). Aside from physician referrals and direct recruitment from clinic, recruitment materials will be distributed or made available to the general public. That is, potential participants may learn about the study and approach or contact the research team directly. We anticipate screening up to 150 potential participants and ultimately enrolling 30 subjects.

At the initial screening visit, investigators will explain the study, provide relevant literature and information, and answer all questions. Written informed consent will be obtained prior to any study-related procedures or interventions. We will indicate that the subjects will receive the same standard of clinical care options regardless of whether they decide to participate in the study. Subjects will be informed that the costs of the surgery are covered by the research study and that participation is voluntary, allowing them to withdraw from the study at any time.

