7 STUDY INTERVENTION DISCONTINUATION AND PARTICIPANT DISCONTINUATION/WITHDRAWAL

7.1 DISCONTINUATION OF STUDY INTERVENTION

Discontinuation from LED-RL phototherapy does not mean discontinuation from the study, and remaining study procedures should be completed as indicated by the study protocol. If a clinically significant finding is identified (including, but not limited to changes from baseline) after enrollment, the investigator or qualified designee will determine if any change in participant management is needed. Any new clinically relevant finding will be reported as an adverse event (AE).

The data to be collected at the time of study intervention discontinuation will include the following:

- Details of any adverse events (e.g., nature, severity, relationship to study intervention, and expectedness) will be documented in the CRFs
- Digital photography of the affected site(s), if applicable

Stopping Rules: Adverse events, serious adverse events, and unanticipated problems (as described in *Section 8: Study Assessments and Procedures*) will be monitored and the trial will be halted early if necessary to protect subjects. Any life threatening events and/or deaths (grade 4 and 5 toxicity) attributable to the study protocol will result in halting the study.

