7.2 PARTICIPANT DISCONTINUATION/WITHDRAWAL FROM THE STUDY

Participants are free to withdraw from participation in the study at any time upon request, without penalty. For example, the participant may withdraw after receiving the mini-facelift surgery but before starting treatment without being penalized for the procedure-related costs of the mini-facelift surgery.

An investigator may discontinue or withdraw a participant from the study for the following reasons:

- Significant study intervention non-compliance
- Any clinical adverse event (e.g., second-degree or higher skin burning, blistering, swelling, pain, ulceration, change in sensation, muscle weakness, worsening of surgical scar) or other medical condition or situation occurs such that continued participation in the study would not be in the best interest of the participant
- The participant meets an exclusion criterion (either newly developed or not previously recognized) that precludes further study participation
- Unforeseen serious adverse event (e.g., neurological symptoms lasting more than 24 hours) occurs

The reason for participant discontinuation or withdrawal from the study will be recorded on the CRF. Subjects who sign the informed consent form and are randomized but do not receive the study intervention may be replaced. Subjects who sign the informed consent form, and are randomized and receive the study intervention, and subsequently withdraw, or are withdrawn or discontinued from the study, will be replaced only if the enrollment period is still open.

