8.2 SAFETY AND OTHER ASSESSMENTS

Refer to *Section 1.3: Schedule of Activities*, for the sequence of events that should occur during the screening process.

Study Specific Procedures and Evaluations for Safety or Other Purposes

- The subject's medical history will be obtained by interview at the screening visit to screen for exclusion criteria.
- The subject's concomitant medication list will be reviewed at each study visit to screen for prohibited medications.
- A screening photosensitivity test will be conducted prior to enrollment, wherein the potential subject will be exposed to LED-RL for 20 minutes on the non-dominant upper forearm (as recommended by the manufacturer in the Omnilux new-U user guide), and then evaluated 24 hours later for evidence of photosensitivity. Criteria for photosensitivity include, but are not limited to: warmth, erythema, edema, blistering, rash, pain, or discomfort lasting more than 24 hours. If no adverse events occurred, the potential subject is deemed "non-photosensitive" and thus eligible for participation in the study.
- At the screening visit, the mini-facelift surgery will be discussed with the subject, including details of the procedure, risks, benefits, alternative options, expected outcomes, and pre- and post-operative instructions.
- The mini-facelift surgery will be performed in-office under local anesthesia by [name] (co-investigator and board-certified dermatologic surgeon).
- A targeted physical examination of the treatment sites (i.e., the periauricular skin and surrounding areas) will be performed at each study visit.
- Each treatment session will be monitored for any safety issues or adverse events, either reported by the subject or observed by the investigator.
- Subjects will be provided with a daily diary to record any adverse events experienced at home during the 3-week treatment period. Investigators will call subjects on a weekly basis to monitor for adverse events during the same time period.
 - Common expected post-treatment effects of transient (i.e., lasts less than 24 hours) erythema, warmth, or edema at the treated sites will be recorded. However, any occurrence of these expected effects will not be considered an adverse event in safety data reports, unless the effect lasts more than 24 hours or is considered serious.
- An exit questionnaire will be administered at the final study visit to assess for patient-reported outcomes and elicit other feedback.

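### Harms of the study-provided mini-facelift are recorded but not fully analysed: the safety set leaves out subjects who are operated on and never start LED-RL

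*Combined protocol and SAP*

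**What the plan says.** **Analysis set.** Section 9.3 states: "Safety analysis dataset: participants who received at least one dose of the study intervention". The Section 1.3 schedule has a row "Administer study intervention (LED-RL and mock therapy)" and a separate row for the mini-facelift, so surgery does not count as a dose.

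**The surgery belongs to the study.** Section 5.5 says subjects will be told that the "costs of the surgery are covered by the research study". Section 2.3.1 lists the surgical risks, including hematoma, infection and wound separation.

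**Operated but untreated subjects are foreseen.** Section 7.2 gives as an example that "the participant may withdraw after receiving the mini-facelift surgery but before starting treatment". It also allows replacement of randomized subjects who receive no study intervention.

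**Causality.** Section 8.3.3.2: "All AEs must have their relationship to study intervention assessed by the clinician who examines" and evaluates the participant. The scale is set against the study intervention, and study procedures enter as one of the other etiologies to consider. Section 7.1 uses a wider term: grade 4 and 5 events "attributable to the study protocol will result in halting the study".

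**Contact.** In Section 1.3 the row "Adverse event review and evaluation" is marked at Enrollment and at Visits 2 to 13 but not at Visit 1, the day of surgery. Section 8.2: "Subjects will be provided with a daily diary to record any adverse events experienced at home during the 3-week treatment period". The weekly calls cover the same period. Section 8.3.4 asks for an adverse event inquiry at every study visit, looking back to the previous one.

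**The concern.** Surgery is the most invasive procedure in the trial, and every subject has it before any LED exposure. The safety set, however, is defined by LED exposure. Subjects lost between the two are not a random sample if a surgical complication is why LED-RL was never started. Tables built on that set would then describe a group selected for a better surgical course, and with 30 subjects one missing event visibly changes a table. In addition, no adverse event contact is scheduled between the operation and the first LED session, which falls at POD 4 to 8.

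**Working it through.** The documents state no expected number of operated but untreated subjects, so there is no planned figure to reproduce. The check is of the text, followed by arithmetic for scale.

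**Step 1: who is outside the set.** Randomization is at Enrollment, surgery at Visit 1, and the first LED/mock session at Visit 2 (Section 1.3). A subject who stops between Visits 1 and 2 is randomized, hence in the ITT set of Section 9.3, but has had no dose, hence is not in the safety set. The same holds for a subject who has no LED-RL but stays for follow-up, which Section 7.1 allows in saying that stopping LED-RL does not end participation.

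**Step 2: can the exclusion depend on surgical outcome?** Two routes follow from the protocol's own rules.
- *Wound separation.* Section 2.3.1 says non-intact skin will not be treated. Open wounds on the face or neck are an exclusion criterion (Section 5.2), and a newly developed exclusion criterion is a ground for withdrawal (Section 7.2).
- *Infection.* Tetracyclines and quinolones are prohibited unless the investigators approve them (Section 6.5). A subject who needs a prohibited medication as standard of care is withdrawn early (Section 5.3).

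**Step 3: do the tables use this set?** Section 9.4.4 counts subjects with adverse events by treatment group and names no analysis set. Use of the 9.3 safety set is the natural reading but is not stated. There is no split by onset before or after first LED exposure and no surgical breakdown. The term treatment-emergent is used without a definition.

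**Step 4: size.** Inputs: 30 subjects and 10% dropout, timing not given (Section 9.2); hematoma 1.1% and infection 0.3% (Section 2.3.3, for facelift surgery). Let k be the number operated but never treated. The documents do not give k; the range 0 to 3 is assumed, where 3 = 0.10 × 30 places all dropout before session 1. With p = 0.011 + 0.003 = 0.014 (no overlap, and excluded subjects at average risk):

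| k | Safety set (30 − k) | Excluded (k/30) | Chance of at least one event among the k: 1 − (1 − 0.014)^k |
|---|---|---|---|
| 0 | 30 | 0% | 0% |
| 1 | 29 | 3.3% | 1.4% |
| 2 | 28 | 6.7% | 2.8% |
| 3 | 27 | 10.0% | 4.1% |

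The last column is too low if complications cause the withdrawals. The documents give no figure for how much too low. Replacement under Section 7.2 could also raise the number operated above 30.

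**Step 5: surgery to Visit 2.** The diary and weekly calls start with the treatment period, when subjects already attend three times a week. For the 4 to 8 days before it, the only planned capture is the look-back at Visit 2. The narrative list of Visit 1 procedures in Section 1.3 has no adverse event item either, so the blank cell and Section 8.3.4 disagree.

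**The case against.** The strongest reply is that the safety objective concerns LED-RL (Section 3), for which a set defined by at least one LED dose is the right one, and that surgical events are not lost. They are recorded from consent whatever their cause, with a look-back at each visit (8.3.4). SAEs are reported at once whether or not related to LED-RL (8.3.6). All adverse events go to the monitors (8.3.5), and the independent safety monitor reviews them as they arise (10.1.6). Section 9.4.4 also presents events leading to premature discontinuation, and 9.4.8 lists individual data. Attrition is expected to be low (4.2, 5.5).

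Most of this stands. Oversight during the trial does not depend on the safety set, and that set should be kept for LED-RL. What remains is that no planned summary has all operated subjects as its denominator. The discontinuation display would not show an event in someone who left for another reason, or who stayed for follow-up without LED-RL.

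Three stronger readings are not supported:
- *That the halting rule cannot be applied to surgery.* Section 8.3.3.2 requires a documented alternative etiology for a rating of not related and requires study procedures to be considered, so a surgical cause would be on record. Nothing in 7.1 ties the rule to the LED causality grade, and unanticipated problems are judged against participation in the research (8.4.1).
- *That the days after session 9 are unobserved.* The sample schedule as legible ends at POD 21, so a session 9 date of POD 23 is an inference. If treatment starts at POD 5, three calendar weeks run to POD 25, leaving two diary days after POD 23. Visit 11 also asks about events since the previous visit.
- *That there is about a one-in-three chance of losing an event.* 1 − 0.986^30 = 34.5% is the chance of a hematoma or infection among all 30 operated subjects, not among those excluded.

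**Conclusion.** The point holds as a gap in analysis, with a smaller gap in scheduled contact. A randomized subject who has the study-provided operation and no LED session is outside the safety set, and the protocol's own rules allow a surgical complication to be the reason. That the event then goes missing from the tables assumes that the 9.3 set governs 9.4.4. On the assumed range, 0% to 10% of operated subjects are excluded. The chance of a hematoma or infection among them is at most about 4% at average risk, and higher by an unknown amount under complication-driven withdrawal. A reader might infer that surgical harms escape the safety plan altogether; the recording and reporting rules contradict that. This is a cheap improvement to the plan, not a failure of subject protection.

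**What to change.** 1. In 9.3 and 9.4.4, add an all-operated set (every randomized subject who has the mini-facelift) and tabulate adverse events for it by onset before or after first LED exposure. Keep the current set for LED-RL safety, and say which set each table uses.
2. On the adverse event form, record whether the documented etiology is surgery or biopsy.
3. Reconcile the blank Visit 1 adverse event cell in 1.3 with the inquiry that 8.3.4 requires at each study visit.
4. Reconcile the terms used for attribution in 8.3.3.2 (study intervention) and 7.1 (study protocol), without changing the halting rule.
5. The sponsor could consider using one of the existing weekly calls for the interval between surgery and Visit 2, since the treatment period already has three visits a week.

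The cost is one extra table, one form field and protocol wording. No visits or subjects are added, and the number of calls need not change.
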